## 1. Protocol Synopsis

**Title of Study:**

A Safety, Tolerability, and Pharmacokinetic Study of Injections of LY3074828 Solution Using Investigational 1-mL Pre-filled Syringes and Investigational 2-mL Autoinjector in Healthy Subjects

**Rationale:**

Study I6T-MC-AMAR (AMAR) will assess the pharmacokinetics (PK), safety and tolerability of, and pain associated with, a 250-mg subcutaneous (SC) dose of LY3074828 solution formulation administered using an investigational manual pre-filled syringe (PFS) or an investigational autoinjector (AI). The administration by AI will be a 1 x 2-mL 125-mg/mL fast-speed injection and the administration by PFS will be 2 x 1-mL 125-mg/mL injections. Both methods of administration will be evaluated at 3 different injection sites (arm, thigh, and abdomen) in order to expand the options for administration in patient use. The study will provide data to bridge PFS administration (as used in Study I6T-MC-AMAE [AMAE]) of LY3074828, a monoclonal antibody, with the investigational AI device planned for use in subsequent studies and patient use.

**Objectives/Endpoints:**

Objectives	Endpoints
Primary 

• To evaluate the PK after administration of 250-mg doses of LY3074828 solution formulation using 2 x 1-mL PFS and 1 x 2-mL AI injections in healthy subjects.

• To assess the safety and tolerability of LY3074828 in healthy subjects.

• To assess pain associated with LY3074828 PFS and AI SC administrations in healthy subjects at 3 different injection sites (arm, thigh, and abdomen).

	

• The primary PK endpoints will be the <math>C_{max}</math>, <math>AUC(0-t_{last})</math>, and <math>AUC(0-\infty)</math> of LY3074828.

• Incidence of TEAEs.

• VAS pain score.

Abbreviations: AI = autoinjector;  $AUC(0-\infty)$  = area under the concentration versus time curve from time zero to infinity;  $AUC(0-t_{last})$  = area under the concentration versus time curve from time zero to time  $t$ , where  $t$  is the last sample with a measurable concentration;  $C_{max}$  = maximum observed drug concentration; PFS = pre-filled syringe; PK = pharmacokinetic; SC = subcutaneous; TEAE = treatment-emergent adverse event; VAS = visual analog scale.

**Summary of Study Design:**

Study I6T-MC-AMAR (AMAR) is a single-center, randomized, parallel-arm, open-label, Phase 1 single-dose study of LY3074828 solution formulation in healthy subjects. Pharmacokinetics, safety and tolerability of, and pain associated with, 250-mg SC doses administered using a PFS or an investigational AI at 3 different injection sites will be evaluated.

Subjects will be randomized to a 2 x 1-mL PFS arm, thigh, or abdomen administration or a 1 x 2-mL AI arm, thigh, or abdomen administration. Subjects will report to the clinical research unit (CRU) on Day -1 and will remain at the CRU until the scheduled procedures have been completed on Day 2. Study drug will be administered by investigative site staff by SC injection per the randomization scheme in the morning of Day 1 after an overnight fast. Subjects will be followed for 12 weeks following dose administration.

Safety and tolerability will be assessed by clinical laboratory tests, vital sign measurements, 12-lead electrocardiograms, recording of adverse events and product complaints, physical examinations/medical assessments, immunogenicity, and injection-site assessments. Pain assessments will be made using an injection-site pain visual analog scale (VAS).

**Dosing Regimen Arms and Duration for an Individual Subject:**

Subjects will receive a 250-mg SC dose of LY3074828 and will be randomized to 1 of 6 dosing regimen arms:

- Test 1: 250 mg LY3074828 solution formulation, 1 x 2-mL 125-mg/mL AI injection administered in the arm
- Test 2: 250 mg LY3074828 solution formulation, 1 x 2-mL 125-mg/mL AI injection administered in the thigh
- Test 3: 250 mg LY3074828 solution formulation, 1 x 2-mL 125-mg/mL AI injection administered in the abdomen
- Reference 1: 250 mg LY3074828 solution formulation, 2 x 1-mL 125-mg/mL PFS injections administered in the arm
- Reference 2: 250 mg LY3074828 solution formulation, 2 x 1-mL 125-mg/mL PFS injections administered in the thigh
- Reference 3: 250 mg LY3074828 solution formulation, 2 x 1-mL 125-mg/mL PFS injections administered in the abdomen

Total duration of the study for each subject will be approximately 16 weeks (screening period  $\leq$ 28 days, residential period of 2 days, and outpatient follow-up period of 12 weeks).

**Number of Subjects:**

A total of approximately 66 subjects who fulfill the eligibility criteria will be randomized to 1 of 6 dosing regimen arms, with 11 subjects randomized to each arm to ensure completion of 10 subjects in each. A subject's study participation is considered as complete if he/she receives the study drug as per the protocol requirements and completes all activities up to and including at least Day 57. A maximum of 2 subjects per arm may be replaced if multiple subjects do not complete the study.

**Statistical Analysis:**

The area under the concentration versus time curve (AUC) from time zero to infinity (AUC[0-∞]), AUC from time zero to time t, where t is the last sample with a measurable concentration (AUC[0-tlast]), and maximum observed drug concentration (Cmax) will be log-transformed and analyzed using a linear fixed-effects model. The model will include device and injection location as fixed effects. The dosing regimen differences between Test and Reference arms will be back-transformed to present the ratios of geometric least squares (LS) means and the corresponding 90% confidence interval (CI).

The time to Cmax (tmax) of LY3074828 between Test and Reference arms will be analyzed using a Wilcoxon rank sum test. Estimates of the median difference, 90% CIs, and p-values from the Wilcoxon rank sum test will be calculated.

Additional PK analyses may be conducted if deemed appropriate.

A linear fixed-effects model will be used to analyze the post-injection pain VAS scores. The model will include device and injection location as fixed effects. The LS means and differences in LS means will be presented along with the corresponding 90% CI.

Safety parameters will be listed and summarized using standard descriptive statistics.

Additional safety and tolerability analyses will be performed if warranted upon review of the data.

## 2. Schedule of Activities

## Study Schedule Protocol I6T-MC-AMAR

Procedure	Screening ≤28 days	Days															Comments
		-1	1	2	4 ±1d	8 ±1d	11 ±1d	15 ±2d	22 ±2d	29 ±2d	43 ±2d	57 ±3d	71 ±3d	85/ED ±3d			
Informed consent	X																
Review / confirm inclusion/exclusion criteria	X	X															Any time prior to dosing.
Subject admission to CRU		X															
Subject discharge from CRU				X													
Outpatient visit	X				X	X	X	X	X	X	X	X	X	X			
Randomization			X														Subjects randomized to 1 of 6 dosing regimen arms.
LY3074828 injection			X														Doses administered by investigative site staff.
Stopwatch recording			X														Stopwatch is the source for injection duration capture for PFS and AI.
Medical history	X																
Weight, height, and BMI	X																
Vital signs: blood pressure, pulse rate, temperature (hour)	X	X	0, 6	24	X	X	X	X	X	X	X				X		Times with respect to start of dosing. Single ECGs to be collected. Zero-hour collection within 30 minutes before dosing. Time allowance for 6- and 24-hour time points: ±30 and ±90 minutes, respectively. For vital sign assessments, temperature need only be included at predose and when clinically indicated.
12-lead ECG (hour)	X		0	24											X		
Physical examination / medical assessment	X	X		X									X		X		Full physical examination/medical assessment at screening. Symptom-directed physical examination/medical assessment at all other time points, and as deemed necessary by the investigator.

Procedure	Screening ≤28 days	Days															Comments
		-1	1	2	4 ±1d	8 ±1d	11 ±1d	15 ±2d	22 ±2d	29 ±2d	43 ±2d	57 ±3d	71 ±3d	85/ED ±3d			
AE review	X	X	X	X	X	X	X	X	X	X	X	X	X	X	X	AE only after signing ICF. Product complaints and device-related AEs collected as appropriate.	
QuantiFERON®-TB Gold test	X																
Serology	X															See Appendix 2 for test details.	
Ethanol test and urine drug screen	X	X														May be repeated at the discretion of the investigator. Ethanol test may be measured in blood, urine, or expired air. See Appendix 2 for test details.	
FSH / serum pregnancy test	X	X							X		X		X		X	Serum pregnancy tests for all female subjects at screening. For all women who are considered to be postmenopausal, FSH should be drawn at screening to confirm postmenopausal status as defined in inclusion criterion [1b]. Women with confirmed postmenopausal status at screening are exempted from further pregnancy tests during the study. See Appendix 2 for test details.	
Clinical chemistry, hematology, and urinalysis	X	X			X			X		X		X		X		See Appendix 2 for test details.	
Creatine phosphokinase		X			X			X									
Injection-site assessment for erythema, induration, pruritus, and edema (hour)			0, 0.25	X	X	X	X									Times with respect to start of dosing. Zero-hour assessments within 1 minute following injection. Time allowance for 0.25-hour assessment is ±5 minutes. Additional assessments performed if deemed necessary by the investigator.	
Injection-site bleeding assessment (hour)			0													Time with respect to start of dosing. Zero-hour assessment within 1 minute following injection.	

Procedure	Screening ≤28 days	Days														Comments
		-1	1	2	4 ±1d	8 ±1d	11 ±1d	15 ±2d	22 ±2d	29 ±2d	43 ±2d	57 ±3d	71 ±3d	85/ED ±3d		
Pain assessment (VAS) (minutes)			1, 5, 15													Time points are minutes post-injection as follows: within 1 minute of the end of injection, 5 (±1.5), and 15 (±2) minutes. For 1-mL PFS, the second injection will be administered 20 minutes (±2) after first injection.
LY3074828 pharmacokinetic sampling (hour)			0, 2, 6	24	X	X	X	X	X	X	X	X	X	X	X	Times with respect to start of dosing. Zero-hour collection immediately (within 15 minutes) before dosing. Time allowance for 2-, 6-, and 24-hour time points: ±15, ±30, and ±90 minutes, respectively.
Immunogenicity sample			Predose					X		X		X		X		LY3074828 antibody sample.
Pharmacogenetics sample			X													

Abbreviations: AE = adverse event; AI = autoinjector; BMI = body mass index; CRU = clinical research unit; d = day; ECG = electrocardiogram; ED = early discontinuation; FSH = follicle-stimulating hormone; ICF = informed consent form; PFS = pre-filled syringe; TB = tuberculosis; VAS = visual analog scale.

Site should schedule activities as appropriate. In cases where several study procedures are scheduled at the same time, follow this order of priority for procedures: pharmacokinetic samples, clinical laboratory tests, immunogenicity sample, stored sample, ECG, vital signs, pain assessment, injection-site assessment, such that pharmacokinetic sample collection occurs as close to the nominal collection time as possible. Procedures specified as predose may be performed within 2 hours from planned dosing.

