## 5.2. Number of Participants

A total of approximately 66 subjects who fulfill the eligibility criteria will be randomized to 1 of 6 dosing regimen arms, with 11 subjects randomized to each arm to ensure completion of 10 subjects in each. A subject's study participation is considered as complete if he/she receives the study drug as per the protocol requirements and completes all activities up to and including at least Day 57. A maximum of 2 subjects per arm may be replaced if multiple subjects do not complete the study.

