## 7. Dosing Regimens

### 7.1. Dosing Regimens Administered

This study will evaluate the PK, safety and tolerability of, and pain associated with 250-mg SC doses administered using 2 x 1-mL PFSs or an investigational 1 x 2-mL AI at 3 different injection sites.

Using the investigational 2-mL AI, the targeted injection duration will be approximately 5 seconds. Manual injections using the PFS should target an injection duration of about 5 to 10 seconds for each 1-mL injection to approximate the injection time range for the AI. The second of the 2 PFS injections should be administered 20 ( $\pm 2$ ) minutes after the first injection to allow for collection of 3 VAS pain score time points prior to administration of the second injection. Approximate injection durations for AIs and PFSs will be obtained using a calibrated stopwatch and recorded in the electronic case report form (eCRF).

Drug and device accountability records will be maintained by the site pharmacy.

Table AMAR.2 shows the dosing regimens for the study.

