**Table AMAR.2. Dosing Regimens Administered**

Dosing Regimen		PFS			AI		
Reference/test	Reference 1	Reference 2	Reference 3	Test 1	Test 2	Test 3	
Injection site	Arm	Thigh	Abdomen	Arm	Thigh	Abdomen	
Product	LY3074828			LY3074828			
Dose	250 mg			250 mg			
Concentration	125 mg/mL			125 mg/mL			
Injection volumes	2 x 1 mL (2 mL total)			1 x 2 mL (2 mL total)			
Number of injections	2			1			
Injection duration	5 to 10 seconds per injection			Approximately 5 seconds			
Formulation and presentation	Solution in a PFS			Solution in an AI			

Abbreviations: AI = autoinjector; PFS = pre-filled syringe.

The PFSs and investigational AIs containing LY3074828 will be supplied fully assembled to the clinical site by Lilly.

Injections, whether administered by PFS or AI, will be given into the arm, thigh, or lower quadrant of the abdomen. For PFS administrations requiring 2 injections, subjects randomized to a group with the arm or thigh as the injection site will have both injections administered to the same limb (same arm or same thigh). Subjects randomized to the group with the abdomen as the injection site will have the 2 PFS injections administered to separate lower quadrants (right and left) of the abdomen. Investigational product will be administered to subjects on-site by designated trained clinical site personnel.

Prior to the PFS or AI injection, the investigator or his/her designee will prepare the subject's skin per Instructions for Use (IFU). Injections into the arm, thigh, or abdomen will be administered by investigative site staff according to the instructions provided by the sponsor. All study injection sites will be marked using a template for size and with a surgical marker in order to identify study injection sites for later assessments. Further information regarding SC administration will be included in the device IFU for the PFS and in the device IB (which contains IFU) for the AI.

In some cases, the site may destroy the material if, during the investigative site selection, the evaluator has verified and documented that the site has appropriate facilities and written procedures to dispose of clinical trial materials.

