### **7.2.1. *Selection and Timing of Doses***

The actual time of all dose administrations (including both the first and second of the 2 PFS injections) will be recorded in the subject's eCRF.

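### Read literally, the 0.25-hour site check falls between 12 minutes before and 2 minutes after the second PFS injection, leaving the second PFS site without a scheduled 15-minute check

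*Protocol*

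**What the plan says.** **Site checks.** In Protocol Section 2, the row for erythema, induration, pruritus and edema has Day 1 checks at 0 and 0.25 hours, then checks on Days 2, 4, 8 and 11. Its comment reads: "Times with respect to start of dosing. Zero-hour assessments within 1 minute following injection. Time allowance for 0.25-hour assessment is ±5 minutes". It adds: "Additional assessments performed if deemed necessary by the investigator".

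**Bleeding.** There is one scheduled time, 0 hours on Day 1: "Time with respect to start of dosing. Zero-hour assessment within 1 minute following injection". Protocol 9.4.4.4 has all injection sites observed at the scheduled times.

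**PFS dosing.** The pain row states: "For 1-mL PFS, the second injection will be administered 20 minutes (±2) after first injection". Protocol 7.1 says that the gap is there "to allow for collection of 3 VAS pain score time points prior to administration of the second injection". The two PFS sites are distinct. Subjects in the abdomen arm "will have the 2 PFS injections administered to separate lower quadrants (right and left) of the abdomen"; in the arm and thigh groups both injections go into the same limb. On recording, Protocol 7.2.1 says: "The actual time of all dose administrations (including both the first and second of the 2 PFS injections) will be recorded".

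**Reporting.** Protocol 10.3.1.2.3 summarises the site findings by device and injection site and lists bleeding. SAP 8.4.7 gives frequency tables, and SAP 8.4.8 lists bleeding. For pain, Protocol 10.3.1.2.1 makes the 1- and 5-minute VAS scores primary, and SAP 8.4.9 models each one separately by device and location.

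**The concern.** An AI subject has one site and one clock. A PFS subject has two sites injected about 20 minutes apart, yet the Schedule gives one Day 1 series of site checks. If that series runs from the first injection, the 15-minute look is made at the first PFS site and at every AI site, but not at the second PFS site.

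Injection-site reactions are adverse events of special interest (Protocol 9.2.1.2), and the study compares devices. Under Protocol 9.4.4.3, questionnaire findings become adverse events only if they are clinically significant or volunteered, so the scheduled check is the main route by which mild early findings are recorded. A check missing for one device only would make its early Day 1 findings look fewer than they are.

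A smaller, separate gap concerns pain. Neither document says whether VAS is repeated after the second PFS injection, or which PFS score enters the 1- and 5-minute models.

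**Working it through.** All times are minutes from the start of the first PFS injection.

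**1. The plan's own figure.** Protocol 7.1 says the 20-minute gap leaves room for three VAS scores before the second injection.
- Longest targeted PFS injection: 10 s = 0.17 min (Protocol 7.1).
- Latest 15-minute VAS: 15 + 2 = 17 min after the end of injection (Section 2).
- Latest time: 0.17 + 17 = 17.17 min. Earliest second injection: 20 − 2 = 18 min.
- 17.17 < 18, so the stated purpose is met. The gap was set with VAS in mind.

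**2. The same arithmetic for the site check.**
- 0.25 h check: 15 − 5 = 10 to 15 + 5 = 20 min.
- Second injection: 20 − 2 = 18 to 20 + 2 = 22 min.
- Earliest check relative to the second injection: 10 − 22 = −12 min.
- Latest check relative to the second injection: 20 − 18 = +2 min.
- At nominal times: 15 − 20 = −5 min, so a check made on time precedes the second injection.

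**3. What a 15 (±5) minute check of the second site would need.** From 18 + 10 = 28 to 22 + 20 = 42 min. This does not overlap 10 to 20 min. After the 0.25 h check, the next scheduled look at the second site is Day 2.

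**4. How many sites.** The protocol plans six arms, "with 11 subjects randomized to each arm to ensure completion of 10 subjects in each".
- AI: 3 arms × 11 subjects × 1 site = 33 sites.
- PFS: 3 arms × 11 subjects × 2 sites = 66 sites, of which 33 are second sites.
- On the single-clock reading, about 33 of 33 + 66 = 99 sites have no scheduled 15-minute check, all of them PFS. Replacements could change the count slightly.

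**5. Which clock governs.**
- *For one clock from the first injection:* the PK row uses the same start-of-dosing phrase for a single 0, 2, 6 and 24 h series. The VAS row instead counts minutes post-injection, so a different clock was written where one was wanted.
- *For a clock per injection:* the same comment cell ties the 0 h check to the injection, Protocol 7.2.1 counts each PFS injection as a dose administration, and Protocol 9.4.4.4 covers all injection sites.

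The single-clock reading is the stronger one for the 0.25 h check. For the 0 h site and bleeding checks, the text does not settle the matter at the second site.

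**The case against.** The best reply is that a per-injection clock is a fair reading, for the reasons in step 5. Protocol 7.1 also has all study injection sites marked for later assessment. On that reading the second site gets its own 0 and 0.25 h checks and there is no gap. This stands to the extent that the gap is conditional. A reader might infer that the Schedule makes a 15-minute check of the second site impossible, or that 33 of 99 sites certainly lack one. The documents support neither without the single-clock reading.

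Other safeguards also count. The investigator may add checks, Protocol Section 9 treats timings as targets, adverse events are reviewed on Days 1 and 2, and both sites are seen from Day 2 to Day 11. SAP 8.4.8 records bleeding within an injection procedure evaluation, which suggests capture tied to each injection but does not prove it. None of these sets a clock for the second site.

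On pain, a reader might infer that both PFS scores would enter the model as independent observations and make the 90% CI too narrow. The documents do not say this. The Schedule shows one series of scores, Protocol 7.1 places three scores before the second injection, and SAP 8.4.9 refers to a score in the singular. The first-injection score is the natural reading, and with one value per subject the planned device and location model is sound.

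**Conclusion.** The point holds in a conditional form. If start of dosing means the first injection, which is the better reading, the 0.25 h check falls from 12 minutes before to 2 minutes after the second PFS injection. About 33 second PFS sites then have no scheduled 15-minute check, while all 33 AI sites do. The clock for the 0 h site check and the single bleeding check at the second site is ambiguous.

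The likely consequence is uneven recording of early Day 1 site findings, against the PFS arms only. It is limited because the site tables are descriptive, bleeding is only listed, and later checks cover both sites. A reader might go further and put a figure on the lost incidence. That would require assuming that the 0 h check also misses the second site, and would need per-site rates that the documents do not give.

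The VAS matter is missing detail, not an error in the model. It deserves a sentence because a first-injection score sets pain after 1 mL by PFS against pain after 2 mL by AI. The TFL shells and eCRF were not available and may already settle it.

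**What to change.** 1. In the Schedule of Activities, time the 0 and 0.25 h site checks and the bleeding check from the end of each injection, and record the injection number. Reconcile the Schedule comments with Protocol 7.2.1 and 9.4.4.4 so that all three use the same clock.
2. Tabulate site findings per subject and per injection. A PFS subject has two sites at which a finding can arise and an AI subject has one, so each table answers a different question.
3. As a minor clarification in SAP 8.4.9, state whether VAS is repeated after the second PFS injection, and name the single PFS value per subject that enters the 1- and 5-minute models. This is best done before the interim VAS summary. The choice of value is the sponsor's.

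**Cost.** One more short site check in about 33 PFS subjects who are already resident on Day 1, and an injection-number field beside the two injection times that the eCRF already records. If a per-injection clock was always intended, only the wording changes. The SAP edit is a sentence or two, and the planned model stays as it is.

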### 3. Introduction

#### 3.1. Study Rationale

Study I6T-MC-AMAR (AMAR) will assess the pharmacokinetics (PK), safety and tolerability of, and pain associated with a 250-mg subcutaneous (SC) dose of LY3074828 solution formulation administered using an investigational manual pre-filled syringe (PFS) or an investigational autoinjector (AI). The administration by AI will be a 1 x 2-mL 125-mg/mL injection and the administration by PFS will be 2 x 1-mL 125-mg/mL injections. Both methods of administration will be evaluated at 3 different injection sites (arm, thigh, and abdomen) in order to expand the options for administration in patient use. The study will provide data to bridge PFS administration (as used in Study I6T-MC-AMAE [AMAE]) of LY3074828, a monoclonal antibody, with the investigational AI device planned for use in subsequent studies and patient use.

